## Appendix 2. Liver Safety: Suggested actions and follow-up assessments and study drug rechallenge guidelines

## Potential Cases of Drug-Induced Liver Injury

Humans exposed to a drug who show no sign of liver injury (as determined by elevations in transaminases) are termed "tolerators," while those who show transient liver injury but adapt are termed "adaptors." In some participants, transaminase elevations are a harbinger of a more serious potential outcome. These participants fail to adapt and therefore are "susceptible" to progressive and serious liver injury, commonly referred to as DILI. Participants who experience a transaminase elevation above 3 × the upper limit of normal (ULN) should be monitored more frequently to determine if they are "adaptors" or are "susceptible."

Liver function tests (LFTs) are not required as a routine safety monitoring procedure in this study. However, should an investigator deem it necessary to assess LFTs because a participant presents with clinical signs/symptoms, such LFT results should be managed and followed as described below

In the majority of DILI cases, elevations in AST (aspartate aminotransaminase) and/or ALT (alanine aminotransaminase) precede total bilirubin elevations (> 2 × ULN) by several days or weeks. The increase in total bilirubin typically occurs while AST/ALT is/are still elevated above 3 × ULN (ie, AST/ALT and total bilirubin values will be elevated within the same laboratory sample). In rare instances, by the time total bilirubin elevations are detected, AST/ALT values might have decreased. This occurrence is still regarded as a potential DILI. Therefore, abnormal elevations in either AST or ALT in addition to total bilirubin that meet the criteria outlined below are considered potential DILI (assessed per Hy's law criteria) cases and should always be considered important medical events, even before all other possible causes of liver injury have been excluded.

The threshold of laboratory abnormalities for a potential DILI case depends on the participant's individual baseline values and underlying conditions. Participants who present with the following laboratory abnormalities should be evaluated further as potential DILI (Hy's law) cases to definitively determine the etiology of the abnormal laboratory values:

- Participants with AST/ALT and total bilirubin values within the normal range who subsequently present with AST/ALT values ≥ 3 × ULN AND a total bilirubin value ≥ 2 × ULN with no evidence of hemolysis and an alkaline phosphatase value < 2 × ULN or not available.

- For participants with baseline AST OR ALT OR total bilirubin values above the ULN, the following threshold values are used in the definition mentioned above, as needed, depending on which values are above the ULN at baseline:
  - Preexisting AST/ALT baseline values above the normal range: AST/ALT values ≥ 2 times the baseline values AND ≥ 3 × ULN; or ≥ 8 × ULN (whichever is smaller).

 Preexisting values of total bilirubin above the normal range: total bilirubin level increased from baseline value by an amount of ≥ 1 × ULN or if the value reaches ≥ 3 × ULN (whichever is smaller).

Rises in AST/ALT and total bilirubin separated by more than a few weeks should be assessed individually based on clinical judgment; any case where uncertainty remains as to whether it represents a potential Hy's law case should be reviewed with the sponsor.

The participant should return to the investigator site and be evaluated as soon as possible, preferably within 48 hours from awareness of the abnormal results. This evaluation should include laboratory tests, detailed history, and physical assessment.

In addition to repeating measurements of AST and ALT and total bilirubin for suspected Hy's law cases, additional laboratory tests should include albumin, creatine kinase, direct and indirect bilirubin, gamma-glutamyl transferase, prothrombin time/international normalized ratio, eosinophils (%), and alkaline phosphatase. Consideration should also be given to drawing a separate tube of clotted blood and an anticoagulated tube of blood for further testing, as needed, for further contemporaneous analyses at the time of the recognized initial abnormalities to determine etiology. A detailed history, including relevant information, such as review of ethanol, acetaminophen/paracetamol (either by itself or as a coformulated product in prescription or over-the-counter medications), recreational drug, or supplement (herbal) use and consumption, family history, sexual history, travel history, history of contact with a jaundiced person, surgery, blood transfusion, history of liver or allergic disease, and potential occupational exposure to chemicals, should be collected. Further testing for acute hepatitis A, B, C, D, and E infection, total bile acids, liver imaging (eg, biliary tract), and collection of serum samples for acetaminophen/paracetamol drug and/or protein adduct levels may be warranted.

All cases demonstrated on repeat testing as meeting the laboratory criteria of AST/ALT and total bilirubin elevation defined above should be considered potential DILI (Hy's law) cases if no other reason for the LFT abnormalities has yet been found. Such potential DILI (Hy's law) cases are to be reported as SAEs, irrespective of availability of all the results of the investigations performed to determine etiology of the LFT abnormalities.

A potential DILI (Hy's law) case becomes a confirmed case only after all results of reasonable investigations have been received and have excluded an alternative etiology.

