#### 1. INTRODUCTION

## 1.1. Disease Background

#### 1.1.1. Sickle Cell Disease

Sickle cell disease (SCD) is an inherited blood disorder caused by a point mutation in the β globin gene resulting in the formation of "sickle hemoglobin" (HbS), which polymerizes in the deoxygenated state and leads to red blood cell (RBC) sickling. The disease is marked by the pathophysiologic features of hemolytic anemia, vaso-occlusion, and progressive endorgan damage, with a clinical course characterized by life-long disability and early death (Gladwin, 2014; Nouraie, 2013). In addition to unpredictable and recurrent vaso-occlusive pain episodes, hemolytic anemia directly damages blood vessels, resulting in a systemic vasculopathy that leads to chronic and progressive tissue and organ injury (Kato, 2007). With improved survival in children, the natural history of SCD has shifted from a disease of childhood to a chronic, debilitating disease of young and middle-aged adults. Cumulative injury to multiple organ systems from repeated episodes of RBC sickling, vaso-occlusion, and chronic hemolytic anemia exact a high clinical burden in the aging adult, significantly impacting quality of life (QOL) and overall functioning (Swanson, 2011).

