The pathogenesis of leg ulcers in SCD is complex and not fully understood. Microvascular occlusion by dense sickled RBCs, reduced oxygen-carrying capacity from anemia, and vascular endothelial damage due to ischemia, hemolysis, and depletion of nitric oxide have been implicated (Bartolucci, 2012; Ballas, 1991; Kato, 2007). Individuals with SCA and leg ulcers have exhibited laboratory markers of particularly severe hemolytic anemia, including lower hemoglobin (Hb) and higher reticulocyte counts, serum lactate dehydrogenase (LDH), bilirubin, and aspartate aminotransferase (AST) than SCA patients without leg ulcers (Nolan, 2006; Taylor, 2008; Cumming, 2008). They also have a higher incidence of severe SCD complications, including stroke, renal impairment, and elevated tricuspid jet regurgitation, compared to SCA patients without leg ulcers (Minniti, 2014). These epidemiologic associations with leg ulcers support a common pathogenesis driven by HbS polymerization and are linked to anemia and hemolysis-associated vasculopathy (Kato, 2007). Histopathologic findings in SCD leg ulcers showing blood vessel occlusion, activated endothelium, thickened intima and luminal distortion as well as capillary proliferation are consistent with severe vasculopathy (Minniti, 2014).

Leg ulcers are a well-recognized debilitating complication of SCD, yet there are still no specific guidelines for management nor effective treatments. This remains a large unmet need for these patients. In a Cochrane review of five randomized trials of interventions for

treating leg ulcers in patients with SCD, none of the therapies resulted in complete ulcer healing (Marti-Carvajal, 2014). Although hydroxyurea (HU)/hydroxycarbamide (HC) and chronic transfusions are used to treat SCD, no controlled studies have demonstrated efficacy of these therapies in the treatment of leg ulcers. Current management of SCD leg ulcers thus relies primarily on the practice approach used for other cutaneous ulcers, involving debridement, wet to dry dressings, and topical agents.

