## 1.4. Summary of the Known and Potential Risks and Benefits of Voxelotor

Voxelotor is well tolerated in adult and pediatric participants 4 years of age and older with SCD. Adverse events, primarily associated with underlying disease and gastrointestinal events, were generally low grade in severity, were managed by dose reduction and/or symptomatic treatment, and seldom resulted in discontinuation of therapy. Identified risks, which include the adverse drug reactions of diarrhea, abdominal pain, nausea, rash, and drug hypersensitivity, were low grade in severity and clinically manageable.

In the pivotal Phase 3 study, Study GBT440-031, voxelotor was shown to significantly increase Hb, improve anemia, and reduce clinical measures of hemolysis in adult and pediatric participants 12 years of age and older with SCD.

In conclusion, voxelotor has a favorable benefit-risk profile based on clinical data from studies enrolling participants 4 years of age and older with SCD. Overall, by inhibiting HbS polymerization voxelotor has the potential to alter the clinical course of the disease by improving anemia and hemolysis in SCD disease.

Further information regarding the potential benefits and risks of voxelotor and guidance for the investigator are provided in the current version of the IB.

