#### 6.6.2. Laboratory Data

All hematology and chemistry laboratory assessments were performed by a central laboratory. Laboratory data will be converted into SI for the analysis. The protocol-specified clinical laboratory (Table 2) findings will be summarized using descriptive statistics by treatment group, without any imputation.

Descriptive statistics will be presented for baseline, each evaluation post baseline, and change from baseline for each post baseline evaluation through 28 days after last dose date.

Laboratory abnormalities will be graded via the Common Terminology Criteria for Adverse Event (CTCAE) or protocol defined severity classification. Laboratory abnormality shifts from baseline will be summarized by treatment group and by reporting periods.

To assess liver injury, a listing of the participants potentially meeting Hy's Law criteria and E-DISH plots will be produced.

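### The Hy's law definition depends on an undefined hemolysis clause and on total bilirubin, in a trial where every participant has hemolytic disease and the drug reduces hemolysis

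*Protocol*

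**What the plan says.** **The case definition.** The first bullet in Protocol Appendix 2 covers "Participants with AST/ALT and total bilirubin values within the normal range who subsequently present with" AST/ALT of at least 3 × ULN and total bilirubin of at least 2 × ULN, "with no evidence of hemolysis and an alkaline phosphatase value" below 2 × ULN or not available. For participants whose baseline AST, ALT or total bilirubin is above the ULN, "the following threshold values are used in the definition mentioned above, as needed". The replacement bilirubin threshold is the smaller of baseline plus 1 × ULN and 3 × ULN.

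**The population and the drug.** Section 1.1.1 says "The disease is marked by the pathophysiologic features of hemolytic anemia". Section 1.3.1 says that patients with sickle cell anemia and leg ulcers show "laboratory markers of particularly severe hemolytic anemia", including higher reticulocytes, LDH, bilirubin and AST. Section 1.4 says voxelotor was shown to "reduce clinical measures of hemolysis in adult and pediatric participants".

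**When the rules apply.** Appendix 2 says liver function tests "are not required as a routine safety monitoring procedure in this study" and directs its rules at tests ordered because of signs or symptoms. Sections 6.10 and 6.10.2 and Appendix 1 schedule ALT, AST, ALP and total, direct and indirect bilirubin at Screening, Day 1, Week 12, Week 24 and the end-of-study or early-termination visit, and every 12 weeks in continued treatment.

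**The analysis.** SAP 6.6.2 plans a listing of participants who potentially meet Hy's law, and says "E-DISH plots will be produced". It does not state the criteria, or say whether the hemolysis clause applies.

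**The concern.** A hemolysis exclusion helps to separate liver injury from red-cell breakdown when most patients have no hemolysis. Here hemolysis is present at entry. Without a definition, two readers can take the same participant's results and reach opposite conclusions, and both can claim to follow the text.

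Total bilirubin adds a second difficulty. It mixes the direct fraction, which matters for liver injury, with the indirect fraction, which the protocol lists as a hemolysis marker. A drug that reduces hemolysis can lower the indirect part and so mask a rise in the direct part. The criterion is then not the same test in the two arms.

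Potential Hy's law cases must be reported as SAEs (Protocol 7.2.3 and Appendix 2), so the definition affects which events are reported as serious and how the liver outputs in the final report are read. SAP section 2 records that dosing was paused because of the overall number of deaths and that the study was then terminated, so the safety outputs will be read closely.

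**Working it through.** The plan states no figure on this point that could be reproduced. The check sets passages side by side and then does arithmetic on the protocol's own bilirubin thresholds.

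**1. Does the hemolysis clause reach participants with raised baselines?** The second bullet replaces threshold values within the definition above it. It neither removes nor restates the other conditions. On the plain reading, the clause carries over.

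**2. Who could show no evidence of hemolysis?** Inclusion criterion 1 requires HbSS or HbS/β⁰ thalassemia. An exclusion criterion removes anyone with absolute reticulocytes below 100 × 10⁹/L. Section 3.1.3.3 names % reticulocytes, indirect bilirubin and LDH as the markers of hemolysis. By those markers, a reader could find some evidence of hemolysis in almost any participant.

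**3. What if the clause is set aside?** In units of ULN, with baseline total bilirubin b, the threshold is

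T = 2 if b ≤ 1; T = min(b + 1, 3) if b > 1.

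At b = 3, T = min(4, 3) = 3, so the bilirubin limb is met before any study drug is taken. At b = 4 it is exceeded by 1. The case then rests on the AST/ALT limb and the ALP condition, and Section 1.3.1 says AST itself is higher in these patients.

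**4. Does the bilirubin limb depend on treatment?** Let f be the fractional fall in bilirubin on voxelotor. The rise that liver injury must add is

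R = T − b(1 − f).

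The excess over no drug effect is R(f) − R(0) = b × f. The documents give neither b nor f, so both are assumed and scanned.

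| b (× ULN) | T | R, f = 0 | R, f = 10% | R, f = 20% | R, f = 40% |
|---|---|---|---|---|---|
| 0.8 | 2 | 1.20 | 1.28 | 1.36 | 1.52 |
| 1.0 | 2 | 1.00 | 1.10 | 1.20 | 1.40 |
| 2.0 | 3 | 1.00 | 1.20 | 1.40 | 1.80 |
| 2.5 | 3 | 0.50 | 0.75 | 1.00 | 1.50 |
| 3.0 | 3 | 0 | 0.30 | 0.60 | 1.20 |
| 4.0 | 3 | −1.00 | −0.60 | −0.20 | 0.60 |

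A value of zero or below means that the limb is met without liver injury. At b = 2 the excess is 2 × 0.10 = 0.2 to 2 × 0.40 = 0.8 × ULN.

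**5. Is the ratio between arms a usable summary?** No, because it depends heavily on baseline. Assume ULN 1.2 mg/dL and let only the indirect fraction fall.
- Baseline 3.0 (indirect 2.6): the trigger is min(4.2, 3.6) = 3.6. The rise needed is 0.60 with no drug effect, and 0.60 + 2.6 × 0.2 = 1.12 or 0.60 + 2.6 × 0.4 = 1.64 with falls of 20% or 40%. The ratios are 1.87 and 2.73.
- Baseline 2.4 (indirect 2.0): the trigger is 3.6. The rise needed is 1.2, against 1.6 or 2.0. The ratios are 1.33 and 1.67.

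The larger ratios come from a baseline just under the 3 × ULN cap. The difference b × f is the steadier measure.

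**6. Which way does the hemolysis clause push?** If voxelotor reduces hemolysis, a voxelotor participant may more easily be judged free of it. That makes the definition easier to meet on voxelotor, against the effect in step 4.

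**The case against.** A reader might infer that no participant can ever qualify. The documents do not support that. The term is undefined, so an investigator could reasonably take it to mean new or worsening hemolysis. Appendix 2 says thresholds depend on baseline values and underlying conditions, and it sends uncertain cases to the sponsor. It later describes the cases to be reported by their AST/ALT and bilirubin elevations without repeating the clause. These provisions soften the rule but do not repair it. Only numbers are adjusted for baseline, the later text refers back to the definition, and its condition that no other explanation has been found leaves chronic hemolysis available as one.

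A reader might also infer that the definition as a whole favors voxelotor. That is not established, because the bilirubin limb and the hemolysis clause can pull in opposite directions.

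Nor do the documents show that the SAP listing will come out empty or fill with hemolytic crises. SAP 6.6.2 does not cite Appendix 2, and Appendix 2 asks for other causes to be considered. Liver signals also have other routes into the data: clinically significant laboratory abnormalities are recorded as AEs, and graded laboratory shifts are tabulated. Section 1.4 names no liver risk among the identified risks. These points stand, and they limit the severity.

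**Conclusion.** The concern holds at moderate severity. The hemolysis clause is undefined and close to unworkable in this population: it can be used to exclude true cases. Setting it aside leaves a bilirubin limb that participants with a baseline of 3 × ULN or more meet without liver injury, so cases can be over-called. The bilirubin limb is treatment-dependent by b × f, for example 0.2 to 0.8 × ULN at b = 2. That size rests on assumed values of f from 10% to 40% and on an assumed baseline; the documents support only the statement that voxelotor reduces measures of hemolysis. The net direction of bias between arms is unknown. The statement in Appendix 2 that liver tests are not routine also conflicts with the scheduled chemistry.

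**What to change.** **Protocol Appendix 2.** The sponsor should reconcile the hemolysis clause with a population that has hemolysis at entry, and reconcile the statement that liver tests are not routine with Sections 6.10 and 6.10.2 and Appendix 1. No clinical criterion is proposed here. According to SAP section 2, the last visit was on 22 October 2024, so new protocol wording can no longer change what sites did. The SAP change is the one that can still alter the results.

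**SAP 6.6.2.**
- State the exact criteria behind the Hy's law listing.
- Produce the listing and the E-DISH plot on direct bilirubin and as multiples of each participant's baseline, alongside total bilirubin. SAP 2.3.3 already defines a laboratory baseline.
- For each flagged case, show that visit's indirect bilirubin, LDH and reticulocytes.
- Do not drop a case from the listing because hemolysis is present.

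**Cost.** All these laboratory values are in SAP Table 2, so no new data are needed. The price is one more plot and listing, and a few more cases for medical review.

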# 1. VERSION HISTORY

Table 1. Summary of Changes

Version/	Associated	Rationale	Specific Changes
Date	Protocol		
	Amendment		
4/	Protocol	Update for the	
16-Dec-2024	Amendment 3	final CSR	Added a sentence about dose pause and
	22 December		study termination.
	2023		Section 2.3.2:
			
 
Replaced the open label treatment
 

			period with the open label treatment
			extension period
			
 
Clarified the analysis period
 

			Section 2.3.3:
			Clarified the baseline definition for labs
			and vital signs
			Section 3.4.2:
			Added baseline disease characteristics,
			sickle cell disease genotype and
			Hydroxyurea use.
			Section 3.5.1:
			Clarified MedDRA version
			Section 3.5.3:
			Removed the neurological examination.
			Section 4:
			Clarified analysis population.
			Section 6.4:
			Modified Section title and added safety
			subgroup analysis
			Section 6.6:
			Added a sentence for Open-label
			treatment extension period
			Updated the wordings to SCD-related
			and non-SCD related events.
			Added listing of SCD and non-SCD related non-TEAEs.
			Modified vital signs will be evaluated
			through end of study visit.
3/	Protocol	Update to	Section 3.1:
02-Jul-2024	Amendment 3	Section headers	Added the definition of target ulcers.
	22 December	to reflect endpoints and	
	2023	provide clarity	Section 3.3:
		for the analysis.	Added PGI-C and CGI-C questionnaire.
		_	-

PFIZER CONFIDENTIAL TMF Doc ID: 98.03 Page 5 of 43

			Section 6.3
			Added the analysis for the raw score of PROMIS endpoints.
			Modified the analysis for PGI-C and CGI-C.
			Appendix 1:
			Added three exploratory endpoints.
			Appendix 2.1:
			Added a footnote of visit windowing to clarify the Day 1 leg ulcer assessment.
2/	Protocol	Updated to	Sections 2.2, 3.3 and 6.3 and Appendix
26-Jan-2024	Amendment 3	match protocol	
 
Removed detail wordings on
 

	22 December	amendment 3.	PROMIS measures
	2023		Section 2.3 - Updated Figure 1 Study
			schema

I	Update to	
 
Section 2.2 – Added exploratory
 

	Section	endpoints.
l	headers to	•
	reflect	Section 2.3.2 - Added more detail on
	endpoints and	the scenario for subjects who have the
1	provide clarity	
	for the	confirmed at Week 12
	analysis.	00
	dizary 525.	Section 3.1- Added a definition of the
		target ulcer(s).
		imger inter(o).
		Section 3.3 - Changed 'Other' to
		'Exploratory' in the Section title and
		added details on healing at Week 12
		and Week 24 and modified hemolytic
		_
1		parameter.
I		
1		
I		

•	Section 3.4.1- Added details on
	stratification factors

- Section 3.4.2 Added country and site in the baseline variables to be summarized.
- Section 3.5.2 Added Total proteins and Phosphorus in the Serum Chemistry laboratory assessment in Table 2.
- Section 5.2.1- Added details on proportion difference
- Section 5.2.2.1 Removed stratification factors and removed a sentence of difference in LS means as it is mentioned in Sections 6.2 and 6.3.
- Section 5.2.3- Modified wordings for the stratified Cox regression model.
- Section 5.2.4 Updated Appendix 4 from 4.2
- Section 6.1- Removed Appendix 4.1.
- Sections 6.2 and 6.3 Added details on the MMRM and Cox regression model, added 'from baseline' to clarify the endpoint, modified description of covariates, added MMRM analysis for PROMIS and VAS exploratory endpoints and removed the sentence 'Note that...' as it is not needed.
- Section 6.4 Added Sections 6.4.1 and 6.4.2 for the subgroup analysis of primary and secondary endpoints, secondary endpoints for the subgroup analysis and age group and country in the subgroup analysis and added forest plot for the subgroup analysis and pvalues will not be provided.

	
 
Section 6.5 - Added site and region in the baseline summary table and actuall exposure to study drug will be summarized.
 

	
 
Section 6.6.1 - Added SCD- related AEs in the reporting and removed safety database as the table are based on clinical database.
 

	• Section 6.6.2 Payiead lab unit to SI

- Section 6.6.2 Revised lab unit to SI, removed the approach of handling extreme lab values, removed treatmentemergent graded abnormal AEs and shift table for one grade or more from baseline and added Hy's Law and E-DISH plot.
- Section 8 Updated the reference for stratified Cox model and removed reference #7 as not needed.
- Appendix 1 Added subgroup analysis and LS means for PRO PROMIS and VAS endpoints in the analysis type and more details in the main analysis model.
- Appendix 2 Added safety endpoints and modified visit windows and visit windows for laboratory assessments.
- Appendix 3- Added PROMIS T-score conversion table.
- Appendix 4 Removed Appendix 4.1 and modified Appendix 4.2 to 4.
- Appendix 5 Added IRT, SI and TESAE and removed CDARS, HR, QT and QTcF from the table.

